5.5.2.3. Treatment-Emergent prostacyclin associated reactions

Definition: The detailed definition of TE prostacyclin associated reactions (i.e., selected TE-AEs) is given as one of the AESI categories in Section 6.8. In addition, TE-AEs during each period are defined as:

- TE-AEs in the titration period (Section 6.10): Any prostacyclin associated reaction that occurred at or after the initial administration of study intervention through Day 86, or EOT plus 3 days for participants who discontinued study intervention in the titration period.

- TE-AEs in the maintenance period (Section 6.10): Any prostacyclin associated reaction that occurred at or after Day 87 through EOT plus 3 days. Participants who discontinued during the titration period are excluded from the denominator.

Population: All participants included in the STS (A302+A303) and OLS

Study Intervention: Selexipag

Outcome measures: Binary variables, occurrence of TE-prostacyclin associated reactions (Yes/No)

Summary method(s) for outcome measure:

- The same analysis applied for TE-AESI in “Summary method(s) for outcome measure” paragraph (Section 5.5.2.2).
- All TE-prostacyclin associated reactions will also be reported for subgroups by PAH medication at baseline - group 1 (defined in Section 5.6.8)
- All TE-prostacyclin associated reactions will also be reported separately for the titration period and the maintenance period. Participants who entered A303 might have experienced a titration period in A302 and another titration period in A303; in this case the rule in Section 6.10 is followed.
- Total TE subject-years will also reported separately for the titration period and the maintenance period (Section 5.5.1.2).

5.5.2.4. Death

Definition: Any death recorded on the Study completion page of the A302 or A303 CRF.

Population: All participants included in the STS (A302+A303) and OLS

Study Intervention: Selexipag

Outcome measures: Binary variables, occurrence of death (Yes/No):

- Treatment emergent death (until EOT plus 3 days)
- Death up to safety follow-up (until EOT plus 30 days)
- All death (regardless of the time frame)

Summary method(s) for outcome measure:

- Number and percentage of participants who died
- Cause of death (for deaths due to multiple causes, their frequencies will be included in each relevant cause)

The summary of deaths (i.e., until EOT plus 30 days) will also be reported for subgroups by PAH medication at baseline - group 1 (defined in Section 5.6.8). Separate listings of all deaths will be generated for STS (A302+A303) and OLS.

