1.2. Study Design

This is a multicenter, open-label study to assess long-term safety and tolerability of selexipag in participants with PAH.

Participants (males or females aged 18 years or older) from the study A302 were enrolled between 07 July 2010 and 02 September 2014 in this A303 study. This participant population consists of 3 cohorts:

- Cohort 1: Participants who completed the study A302 including the Treatment Extension Period (TEP) as scheduled per protocol (i.e., treated until unblinding of the study) without morbidity event.
- Cohort 2: Participants who experienced a morbidity event (had to be confirmed by the Critical Event Committee [CEC]) during the study A302.
- Cohort 3: Participants who experienced a worsening of PAH during the TEP of A302 and for whom a written approval to enter study A303 had been obtained from the sponsor.

The study is conducted in 155 centers in 39 countries.

Visit 1 in the A303 study should correspond to the last visit in study A302. If this was not possible, Visit 1 had to be performed not later than 2 weeks (14 days) after the last visit in study A302.

Participants of Cohort 2 and Cohort 3 were enrolled in the A303 study without knowledge of their previous treatment to preserve the integrity of the double-blind A302 study. All these participants entered the titration period of A303, i.e., they started selexipag at the lowest dose (200 µg bid).

Participants of Cohort 1 were eligible to enter the A303 study with knowledge of their previous study intervention allocation (selexipag or placebo). Participants who were receiving selexipag in A302 directly entered the maintenance period in A303 at the same dose of selexipag they were receiving at the end of the A302 TEP, except participants who were with treatment interruption ≥ 3 days between studies would enter the titration period of A303. Participants who were receiving placebo in A302 entered first the titration period of A303, i.e., started selexipag at the lowest dose (200 µg bid). Participants with a treatment interruption of at least 3 days between both studies (irrespective of whether randomized to selexipag or placebo) also entered the titration period of A303.

Treatment in the titration period of A303 was started at a selexipag dose of 200 µg bid with subsequent up-titration by 200 µg bid increments to achieve the individual MTD (maximum

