1600 µg bid) for administration during the maintenance period. Maintenance treatment was planned to continue until the earliest of (1) selexipag becoming commercially available in this indication in the participant's country, (2) the sponsor deciding to stop the A303 study, or (3) the participant or the investigator deciding to discontinue study intervention.

[figure not shown]
Each participant had his/her selexipag dose up-titrated up to his/her individual highest tolerated dose. Participants would receive new medication bottles at Visit 1, Visit 5 and every 6 months until the end of the A303 study. If a participant would enter the titration period, additional medication bottles would be given at Visit 2, 3, and 4.

At the end of the open-label study or after permanent discontinuation of study intervention, the end of study (EOS) visit will be performed and a post-treatment safety follow-up period will follow (30 days as recommended in the protocol; this is the last planned contact date).

The Data Monitoring Committee involved in the study A302 have reviewed safety data from A303 study up to 01 July 2016 (date of disbandment of the committee).

No interim analysis was planned in the protocol.

Figure 1: Study design

Titration period was applied to participants with a morbidity event or PAH worsening during TEP, participants on placebo in study AC 065A302 and participants with treatment interruption ≥ 3 days between studies (Figure 1 above). More information about Titration period can be found in Sections 5.5.1.1 and 5.5.2.3.

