5.5.1.2. Treatment-emergent Exposure Durations

For estimating the average annualized event rates of treatment-emergent adverse events of special interest (Section 5.5.2.2 and 5.5.2.3), the treatment-emergent (TE) exposure durations (in days) of individual participants are required and calculated as [EOT+ 3 days] – Day 1 + 1 day. The TE exposure duration in months is calculated as (duration in days / 30.4) and in years (also called TE subject-years) as (duration in days / 365.25). The total TE exposure duration of a treatment group is the sum over individual participants of that treatment group, and the average TE exposure duration is the total duration divided by the number of participants of that treatment group.

For prostacyclin associated reactions (Section 5.5.2.3), additional TE exposure durations of individual participants are defined for the titration and maintenance periods.

- The TE exposure duration of the titration period will be calculated as:
 - If the participant did NOT prematurely stop the study intervention before Day 86: TE exposure duration (days) = 86.
 - If the participant prematurely stopped the study intervention before Day 86: TE exposure duration (days) = [EOT+ 3 days] – [Day 1] + 1 (Section 5.1.3).
- The TE exposure duration of the maintenance period will be calculated as:

- If the participant did NOT prematurely stop the study intervention before Day 86: TE exposure duration (days) = {[EOT +3 days] – [Day 1] + 1} – 86 (Section 5.1.3).
- If the participant prematurely stopped the study intervention before Day 86: TE exposure duration will not be calculated, and the participant will be excluded from the denominator.

For a period (titration or maintenance) the TE subject-years of individual participants are calculated as (period-specific duration in days / 365.25). The total TE subject-years for a period of a treatment group is the sum over individual participants included in the respective period of that treatment group.

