5.5.2.2. Adverse Events of Special Interest

Definition: See Section 6.8 for the list of adverse events in each adverse events of special interest (AESI) category. Any AESI occurring at or after the initial administration of study intervention (in STS or OLS – see Section 5.1.3) through EOT plus 3 days is considered as treatment emergent.

Population: All participants included in the STS (A302+A303) and OLS

Study Intervention: Selexipag

Outcome measures: Binary variables, occurrence of each category (Section 6.8) of treatment-emergent adverse events of special interest (TE-AESI), (Yes/No):

Summary method(s) for outcome measure:

- Number and percentage of participants with at least one TE-AESI.
- Number and percentage of participants with at least one TE-AESI leading to discontinuation of study intervention.
- Number and percentage of participants with at least one serious TE-AESI.
- Number and percentage of participants with at least one TE-AESI with a fatal outcome.
- Number of recurrent TE-AESIs (Participants may have multiple preferred terms [PTs] under a TE-AESI or/and multiple occurrences of a PT. The total number of occurrences of any PT in each TE-AESI category will be used).
- Total TE subject-years of treatment (Section 5.5.1)
- Average annualized event rate is calculated as the sum of numbers of recurrent TE-AESIs of individual participants in a treatment group/total TE subject-years of treatment
- Observed PTs (if a participant had multiple occurrences of a PT, this participant is counted only once)
- Severity (if a participant had multiple occurrences of a PT with different severity levels, this participant is counted only once in the worst severity level)

Separate listings of TE-AESIs will be generated for STS (A302+A303) and OLS.

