5.5.2.4.1. Survival Analysis

Definition: Time to death is calculated from the initiation of selexipag in A302 to death. Participants who died after initiation of selexipag are considered having an event. For the remaining participants their times to death are censored, with the censoring date defined as the latest date between date of completion/discontinuation/lost to follow-up and the last contact date (see Section 5.1.4 for definition).

The median follow-up time will be estimated using the reverse Kaplan-Meier (KM) estimate of survival data, i.e., reversing censoring indicator for the KM estimate, with CENS = 0 for death and CENS = 1 for being alive.

Population: Subset of participants who received selexipag in A302 in the STS (A302+A303).

Study Intervention: Selexipag

Outcome measures: Time to death (regardless of the time frame) from start of first selexipag dose to A303 Study Closure

Summary method(s) for outcome measure:

- Descriptive summary (i.e., number of participants at risk, number of participants censored, number of deaths)
- KM estimates with point estimate (%) and 95% confidence limits (CLs). It will be provided at every three months in the 1st year, and every year thereafter. The CLs are constructed using Greenwood's formula (Collett 2014) for the standard error.
- KM estimates will also be displayed graphically. The KM curve will be truncated when less than 10% of the initial participants remain at risk (Pocock 2002).
- Additional subgroup analyses by baseline WHO FC (group 2):
 - Descriptive summary and KM estimates with 95% CLs for each WHO FC (I/II/III/IV).
 - Separate KM curves for WHO FC II and III

A sensitivity analysis for deaths up to EOT + 30 days will be performed as defined in Table 5 below.

Table 5: Sensitivity Analysis

| | |
|---|---|
| - | Population: For participants who died or were known alive after EOT + 30 days, the time to death will be censored at the earliest date between EOT + 30 days and the last contact date (see Section 5.1.3.1 for definition). |
| - | Outcome measures: Time to death from start of first selexipag dose to EOT + 30 days. |
| - | Summary method(s) for outcome measure: Same as survival analysis described above. |

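### Deaths in the open-label columns are planned only as crude counts and percentages, so the 379 ex-placebo participants get no mortality estimate that allows for unequal follow-up

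*SAP*

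**What the plan says.** SAP 5.5.2.4 treats death as a yes/no outcome in three windows: to EOT + 3 days, to EOT + 30 days, and at any time. The summaries are "Number and percentage of participants who died" and cause of death, for both the OLS and the STS. The subgroup table uses the middle window: "The summary of deaths (i.e., until EOT plus 30 days) will also be reported for subgroups by PAH medication at baseline". All deaths are also listed.

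SAP 5.5.2.4.1 is the only time-to-event analysis of death. Its population is the "Subset of participants who received selexipag in A302 in the STS (A302+A303" pooled set), and its clock starts at selexipag initiation in A302, a date that ex-placebo participants do not have. The Table 5 sensitivity version changes only the follow-up rule, so that "the time to death will be censored at the earliest date between EOT + 30 days and the last contact date". It does not add the ex-placebo participants.

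Follow-up differs between participants by design. SAP 1.2 says that participants "were enrolled between 07 July 2010 and 02 September 2014 in this A303 study". Treatment ran until the earliest of "selexipag becoming commercially available in this indication in the" participant's country, a sponsor decision to stop, or discontinuation by the participant or investigator.

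Elsewhere the SAP does adjust for time in these same columns. Section 5.5.2.1 plans exposure-adjusted incidence rates by system organ class and preferred term, and 5.5.2.2 plans annualised rates for adverse events of special interest. The denominators are defined in 5.5.1.2: "The total TE exposure duration of a treatment group is the sum over individual participants of that treatment group".

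**The concern.** The stated objective is long-term safety and tolerability. When participants enter at different dates and stop for different reasons, a percentage dead mixes the mortality rate with the length of observation, and a reader cannot separate the two. The report would give survival over time for those who started selexipag in A302, but for more than half of those treated in A303 it would give only a proportion with no time scale attached. The same holds for the OLS columns as a whole, because the 330 ex-selexipag participants appear in the KM analysis timed from A302 and not from A303 Day 1. It also holds for every PAH-medication subgroup.

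The plan is uneven here: non-fatal events are put on a subject-year basis and all-cause death is not.

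**Working it through.** **1. The plan's own counts (SAP section 4).** Ex-selexipag 330, ex-placebo 379, total A303 709, selexipag in A302 574, all 953.

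- 330 + 379 = 709 and 574 + 379 = 953. Both totals reproduce.
- Ex-placebo share of OLS: 379/709 = 53.5%. Share of STS: 379/953 = 39.8%.
- KM coverage of STS: 574/953 = 60.2%.

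**2. Which planned outputs give time-adjusted all-cause mortality for the 379?**

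| SAP section | Covers the 379? | Uses time? | All-cause death? |
|---|---|---|---|
| 5.5.2.4 Death | Yes | No | Yes |
| 5.5.2.4.1 KM and Table 5 | No | Yes | Yes |
| 5.5.2.1 exposure-adjusted rates | Yes | Yes, to EOT + 3 days | No; by organ class and preferred term |
| 5.5.2.2 special-interest events | Yes | Yes, to EOT + 3 days | No; fatal cases as number and percentage |

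No row has yes in all three columns.

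**3. Entry spread.** 07 July 2010 to 02 September 2014 is 1518 days; 1518/365.25 = 4.2 years. This is for all A303 entrants. The spread among the 379 is not documented.

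**4. What a crude percentage hides.** Deaths/N = (deaths/total time) × (total time/N), that is, rate × mean time at risk. Neither factor is given for the 379, so the following is illustration only. Assume 76 deaths (76/379 = 20.1%) and a mean time at risk of 2, 4 or 6 years.

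| Assumed mean time at risk | Subject-years | Deaths per 100 subject-years (exact Poisson 95% CI) | 3-year survival, exp(−3 × rate) |
|---|---|---|---|
| 2 years | 379 × 2 = 758 | 10.03 (7.90 to 12.55) | 74% |
| 4 years | 379 × 4 = 1516 | 5.01 (3.95 to 6.27) | 86% |
| 6 years | 379 × 6 = 2274 | 3.34 (2.63 to 4.18) | 90% |

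The survival column also assumes a constant hazard. The same printed percentage fits all three rows.

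**5. Would a KM curve for 379 be precise enough?** Without censoring, and with assumed survival from 0.9 down to 0.5, the 95% half-width is 1.96 × √(S(1 − S)/379), or 3.0 to 5.0 percentage points. Simulation with censoring (400 samples per scenario, exponential deaths at 4 to 8 per 100 subject-years, independent exponential censoring giving 2 to 6 years at risk, Greenwood standard error) gave half-widths of 3.5 to 5.9 points for 3-year survival. At 6 per 100 subject-years the mean crude percentage ran 11.9%, 24.0% and 36.2% as time at risk went from 2 to 4 to 6 years, while mean 3-year KM survival stayed at 83 to 84% (true value 83.5%).

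**6. Does the window matter for the denominator?** Going from EOT + 3 to EOT + 30 days adds at most 379 × 27/365.25 = 28.0 subject-years, which is 3.7%, 1.8% or 1.2% of the three totals in step 4. The window therefore matters mainly for which deaths are counted.

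**The case against.** The study is descriptive. Protocol 3.8.2 lists adverse-event endpoints and no mortality endpoint, and Protocol 5.2.2.1 says only that displays for patients who die may be provided. The KM analysis already goes further than that.

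Limiting it to the 574 is also defensible. They are followed from first dose whether or not they entered A303, including the 574 − 330 = 244 who did not. The 379 had to survive A302 and enter A303, and they mix completers with participants who had a morbidity event or PAH worsening. Their curve answers a different, survivor-selected question. This stands. It argues for a separate, footnoted display and against pooling, but it does not make a crude percentage interpretable over time.

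A reader could also divide treatment-emergent deaths by the "Total TE subject-years of treatment (Section 5.5.1") reported by column, since both stop at EOT + 3 days. That is true for the columns, but the SAP does not plan the rate or its interval, and it would not match the EOT + 30 day window of the subgroup death table. The exposure-adjusted rates may be read as covering fatal events, but they give no all-cause total.

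Finally, SAP Table 1 cites a separate SAP on long-term survival and a Summary of Clinical Safety. Neither was supplied, so they may explain the restriction or cover ex-placebo survival. The point is limited to what these two documents plan.

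**Conclusion.** The gap is real and worth closing, as a cheap improvement and not as the correction of an error. In the supplied documents, 379 participants (53% of OLS, 40% of STS) have no planned all-cause mortality estimate that accounts for follow-up, and neither do the OLS columns timed from A303 Day 1 or the PAH-medication subgroups.

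Three stronger readings are tempting, and the documents do not support them:

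- *That the crude percentages favour one column or subgroup.* Time at risk by group is not given, so neither the size nor the direction of any distortion can be determined.
- *That follow-up among the 379 is spread over 4.2 years.* That figure is for all A303 entrants. Ex-placebo completers could enter only after A302 closure and unblinding, and the mix of completers and earlier entrants is not stated.
- *That an any-time KM curve is needed for the ex-placebo group.* Planned contact after treatment in A303 ends at about 30 days (Protocol 3.4.2 and 3.10.5), so long-term survival after EOT would be weakly supported.

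The 20% mortality, the 2 to 6 years at risk and the hazards in the working are assumptions. The half-widths with censoring also assume that censoring is independent of prognosis.

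**What to change.** **Main change, SAP 5.5.2.4.** Add deaths to EOT + 30 days per 100 subject-years, with exact Poisson 95% confidence intervals, for each column and each PAH-medication subgroup. Time runs from the set-specific Day 1 (5.1.3) to death or the earlier of EOT + 30 days and the last contact date (5.1.4). Keep the crude percentages.

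**Supportive change, SAP 5.5.2.4.1.** Add one KM table and figure for the ex-placebo group, from first selexipag dose in A303, censored at EOT + 30 days as in Table 5. Show it separately from the 574 and without the WHO functional class breakdowns.

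**Footnote to both.** A303 entrants had to survive A302; they mix completers with participants who had morbidity events or PAH worsening; censoring may be informative if selexipag is stopped because of worsening; the figures are descriptive and columns are not to be compared.

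**Cost.** No new data are needed, because Day 1, last contact and the censoring rule are already defined. The work is one time-at-risk derivation, up to 5 columns × (1 overall + 4 subgroups) = 25 rates, some in small cells, and one KM output. Deaths after EOT + 30 days stay outside the rate. A single rate averages over a hazard that may change with time, which the KM output would show for the ex-placebo group.

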5.5.2.4.1. Survival Analysis

Definition: Time to death is calculated from the initiation of selexipag in A302 to death. Participants who died after initiation of selexipag are considered having an event. For the remaining participants their times to death are censored, with the censoring date defined as the latest date between date of completion/discontinuation/lost to follow-up and the last contact date (see Section 5.1.4 for definition).

The median follow-up time will be estimated using the reverse Kaplan-Meier (KM) estimate of survival data, i.e., reversing censoring indicator for the KM estimate, with CENS = 0 for death and CENS = 1 for being alive.

Population: Subset of participants who received selexipag in A302 in the STS (A302+A303).

Study Intervention: Selexipag

Outcome measures: Time to death (regardless of the time frame) from start of first selexipag dose to A303 Study Closure

Summary method(s) for outcome measure:

- Descriptive summary (i.e., number of participants at risk, number of participants censored, number of deaths)
- KM estimates with point estimate (%) and 95% confidence limits (CLs). It will be provided at every three months in the 1st year, and every year thereafter. The CLs are constructed using Greenwood's formula (Collett 2014) for the standard error.
- KM estimates will also be displayed graphically. The KM curve will be truncated when less than 10% of the initial participants remain at risk (Pocock 2002).
- Additional subgroup analyses by baseline WHO FC (group 2):
 - Descriptive summary and KM estimates with 95% CLs for each WHO FC (I/II/III/IV).
 - Separate KM curves for WHO FC II and III

A sensitivity analysis for deaths up to EOT + 30 days will be performed as defined in Table 5 below.

Table 5: Sensitivity Analysis

| | |
|---|---|
| - | Population: For participants who died or were known alive after EOT + 30 days, the time to death will be censored at the earliest date between EOT + 30 days and the last contact date (see Section 5.1.3.1 for definition). |
| - | Outcome measures: Time to death from start of first selexipag dose to EOT + 30 days. |
| - | Summary method(s) for outcome measure: Same as survival analysis described above. |

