3.10.4 End of study visit or permanent discontinuation of study drug

Actelion will notify all sites when the end of study will occur. It can be at different dates depending on the sites and/or the country (see definition in Section 1.4.6). For all patients still participating to the study, the EOS visit must be scheduled within 4 weeks after the end of study notification.

For patients prematurely discontinuing selexipag treatment, it is recommended to perform the EOS visit within 7 days of the last study drug intake.

This visit includes:

- Physical examination
- Recording of AEs/SAEs
- Concomitant medication
- Measurement of vital signs and body weight
- Laboratory tests including:
 - Hematology
 - Blood chemistry
- Urine pregnancy test (for women of childbearing potential)
- Return of unused medication including empty bottles.

3.10.5 30-day follow-up

All patients will be contacted by phone 30 to 37 days after study drug discontinuation (safety follow-up call) [Sections 4.2.4 and 4.3.2].

- Urine pregnancy test result for women of childbearing potential

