4.3.4 Reporting of serious adverse events after the 30-day follow-up period

New SAEs occurring at any time after the 30-day follow-up period after study drug discontinuation may be reported on a SAE form to the Actelion drug safety department within 24 hours of the investigator's knowledge of the event, if considered related to the previous exposure to study drug by the investigator. These SAEs are only entered in the drug safety database, and hence will not affect study closure.

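### Survival is labelled as running to A303 Study Closure, but no follow-up to that date is scheduled for all 574 participants, and Table 5 shares the independent-censoring assumption

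*SAP*

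**What the plan says.** The survival population in SAP 5.5.2.4.1 is everyone who received selexipag in A302: 574 by the table layout in SAP section 4, of whom 330 were treated in A303. The outcome is "Time to death (regardless of the time frame) from start of first selexipag dose to A303 Study Closure". The event rule has no time limit: "Participants who died after initiation of selexipag are considered having an event". Survivors are censored "with the censoring date defined as the latest date between date of completion/discontinuation/lost to follow-up and the last contact date".

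Scheduled follow-up differs by group:

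- **Non-entrants.** SAP 5.1.4.1 builds last contact from A302 sources, including a survival follow-up page at A302 closure.
- **A303 entrants.** SAP 5.1.4.2 takes last contact from the A303 study completion page, or from the latest recorded date if that is missing. It lists no survival follow-up page. Protocol 3.10.5 sets the final call: "All patients will be contacted by phone 30 to 37 days after study drug discontinuation". SAP 1.2 describes the same period: "30 days as recommended in the protocol; this is the last planned contact date". Later contact is selective: SAEs ongoing at the end-of-study visit (Protocol 4.3.3) and drug-related discontinuations (Protocol 3.4.2).

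SAP 5.5.2.4 defines a death as "Any death recorded on the Study completion page of the A302 or A303 CRF". After day 30, Protocol 4.3.4 lets the investigator report an SAE considered drug-related, but "These SAEs are only entered in the drug safety database, and hence will not affect study closure".

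Table 5, the only sensitivity analysis, covers deaths to EOT + 30 days. Everyone who died later or was known alive later is "censored at the earliest date between EOT + 30 days and the last contact date (see Section 5.1.3.1 for definition"), and the method is unchanged.

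**The concern.** Kaplan-Meier is unbiased only if a participant who is censored has the same later death rate as one still under observation. Here observation tends to end because treatment or a study ended. Some stopping is administrative, such as commercial availability (Protocol 1.4.6). Some is not: Protocol 3.4.1 names adverse events and the patient's best interest, and Protocol 3.2.4.1 mentions switching to i.v. or s.c. treatment. Higher mortality after such stopping is plausible, although the documents do not establish it.

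No hypothesis test is affected. The yearly survival percentages are themselves the output, and the SAP Introduction says that the completed summary can be used to update the sNDA/MAA tables. A reader would take the stated horizon to mean complete mortality follow-up. The Greenwood limits reflect sampling error and not this bias.

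**Working it through.** The plan states no survival estimate or hazard, so there is no figure to reproduce beyond the counts.

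**1. Counts (SAP section 4).** 330 + 379 = 709; 574 + 379 = 953; 574 − 330 = 244. Entrants are 330/574 = 57.5% of the survival population and non-entrants 42.5%.

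**2. Direction, by hand.** Let h be the on-drug death rate, d the stopping rate and r·h the death rate after stopping. True survival is

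S(t) = e^(−(h+d)t) + [d/(h+d−rh)]·[e^(−rht) − e^(−(h+d)t)].

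If everyone were censored near stopping, Kaplan-Meier would estimate about e^(−ht). With assumed h = 0.05, d = 0.10, r = 2 and t = 5: S = 0.472 + 2 × (0.607 − 0.472) = 0.741, against e^(−0.25) = 0.779. The estimate is nearly 4 points too high. At r = 1 the two agree.

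**3. Model with the two groups.** Simulation, 600,000 subjects per scenario, constant hazards.

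- Assumed: on-drug death 0.05/yr; A303 stopping 0.08/yr; A302 closure uniform 0.5–4.5 years after start; A303 administrative end uniform 5–9 years; entrants followed 33 days after stopping; A302 stoppers followed to A302 closure; no later A303 deaths recorded.
- Set to match the documents: A302 stopping 0.19/yr gives 57.1% entering A303 (documents 57.5%) and median A302 exposure of 18.9 months (SAP Introduction 18.8).
- Simplification: earlier A303 entry after a morbidity event is not modelled.

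| Hazard ratio after stopping | True 5-year survival, % | Main KM, % | Table 5 KM, % | Main error, points |
|---|---|---|---|---|
| 1 | 77.9 | 77.8 | 77.8 | −0.1 (about zero) |
| 2 | 72.4 | 75.3 | 77.7 | +2.9 |
| 4 | 64.0 | 71.0 | 77.2 | +7.0 |

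**4. Which group produces the error (ratios 2 and 4).**

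- A303 entrants followed completely: about +2.1 and +4.8 remain. That is 2.1/2.9 = 72% and 4.8/7.0 = 69% of the total.
- Non-entrants followed onward, A303 call unchanged: about +0.5 and +1.3 remain.
- Rise confined to A303 stoppers: about +0.7 and +1.8.

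Most of the error therefore comes from A302 stoppers censored at A302 closure.

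**5. Range.** Over on-drug death 0.03–0.08/yr or A303 stopping 0.05–0.12/yr, the error is +2.0 to +3.7 at ratio 2 and +5.3 to +8.1 at ratio 4.

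**6. Late deaths that are recorded.** They count as events while comparable survivors are censored earlier, which pulls the estimate down. With 30% of late A303 deaths recorded, the errors are −0.2, +2.4 and +6.1 at ratios 1, 2 and 4. In a separate model where everyone has entrant-type follow-up (death 0.06/yr, stopping 0.10/yr, ratio 2), about 50% capture cancels the error (69.9 against a true 69.7). Full capture reverses it (66.9 against 69.8).

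**7. Table 5.** It stays at 77.2–77.8% while true survival falls from 77.9% to 64.0%, so it does not bound the error. The gap between it and the main result does carry information: 0, 2.4 and 6.2 points at ratios 1, 2 and 4. The main analysis sees A302 stoppers up to A302 closure and Table 5 does not. Both analyses drop A303 stoppers about 30 days after stopping, so the gap says almost nothing about them.

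**8. Latest-date rule.** A discontinuation or loss date without contact can extend survival beyond the last proof of life. With 3–10% lost and a lag of 0.25–1 year, the effect at 5 years is 0.02–0.3 points if only entrants are affected, and up to 0.6 if all 574 are.

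**The case against.** The strongest reply is that the analysis is descriptive and that A303 closure is an ordinary maximum horizon beside a stated censoring rule. Table 5 is described as an analysis of deaths to EOT + 30 days, never as a bound on informative censoring. Readers will also see numbers at risk, censored and dead, a reverse Kaplan-Meier median follow-up, and a curve truncated below 10% at risk (SAP 5.5.2.4.1). SAP 5.2 adds reasons for stopping, and SAP 5.5.2.4 tabulates deaths to EOT + 30 days and at any time, so late deaths can be derived. The CRF pages and the separate SAP for long-term survival labelling were not supplied, so actual capture of late deaths is unknown.

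Much of this stands. It limits the point to a conditional one, and Table 5 is not misdescribed. But none of the planned displays reports known vital status at closure, and no planned analysis relaxes independent censoring.

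Two stronger readings are tempting. A reader might blame the 30 to 37 day call for the whole error; step 4 shows that it accounts for the smaller part. A reader might also infer that agreement between the main result and Table 5 would mean nothing. Step 7 shows that agreement would be evidence against raised mortality among A302 stoppers, and is uninformative only about A303 stoppers.

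**Conclusion.** The point holds in a conditional form. The stated horizon is not matched by follow-up scheduled for all 574 participants, in either group. If mortality is higher after stopping and few late deaths are recorded, the yearly percentages are too high. The illustrative 5-year size is about 0, +2.9 and +7.0 points at ratios 1, 2 and 4, with roughly 70% of it from A302 stoppers. Substantial recording of late deaths, without matching follow-up of survivors, would pull the other way.

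The documents do not show that survival will be overstated: they give no hazards, and the size rests entirely on the assumed rates. The latest-date rule is minor and depends on how sites date a loss. The Table 5 cross-reference is clerical: SAP 5.1.3.1 defines Day 1 and EOT for the open-label set, not last contact.

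**What to change.** - **(a) Censoring.** Censor at the last date the participant is documented alive. A completion, discontinuation, withdrawal or lost-to-follow-up date without contact should not extend survival time.
- **(b) Horizon.** Replace the A303 closure label with the actual one: A302 closure for non-entrants, and about 30 days after stopping for entrants. Report known vital status at closure separately for the 244 and the 330, beside the late deaths derivable from the SAP 5.5.2.4 tables.
- **(c) Exploratory sensitivity analysis.** For participants who stopped for non-administrative reasons, vary the hazard after censoring, for example ×1, ×2 and ×4 of a stated reference hazard. Explicitly include A302 stoppers censored at A302 closure. Define which reasons count as administrative and put unknown reasons, which SAP 5.2 anticipates, in a stated category. Present the result as a range and not as a bound, because the right multiplier is unknown.
- **(d) Clerical.** In Table 5, cite SAP 5.1.4 for last contact date and 5.1.3.2 for EOT.

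The cost is SAP wording, one vital-status table and slight extra programming on data already collected. The survival figures may look less favourable.
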